## **4. Measurement / Instrumentation**

The measures and instruments to be used in the study, along with the planned assessment schedule, are summarized in the table below.

### **4.1. Primary Outcomes**

**4.1.1. Suicide ideation** will be measured using the Scale for Suicide Ideation (SSI), an empirically-supported self-report scale that assesses the intensity of suicide-related thoughts, urges, intentions, and behaviors. All subjects complete the first 5 items. If a subject positively endorses either item 4 (active ideation) or item 5 (passive ideation), they are directed to complete an additional 14 items.

**4.1.2. Suicidal behaviors** will be measured using the Self-Injurious Thoughts and Behaviors Interview-Revised (SITBI-R), an empirically-supported self-report scale that assesses a range of self-injurious behaviors including suicide attempts, interrupted suicide attempts, preparatory behaviors, and non-suicidal self-injury.

## 4.2. Secondary Outcomes

**4.2.1. PTSD symptom severity** will be measured using the National Stressful Events Survey PTSD Short Scale (NSESS), a 9-item self-report scale of PTSD symptom severity. Respondents are directed to rate the intensity of each symptom within the past 7 days on a 5-point scale ranging from 0 (not at all) to 4 (extremely). Items are summed to provide an overall metric of PTSD symptom severity.

**4.2.2. Psychiatric symptom severity** will be measured using the DSM-5 Self-Rated Level 1 Cross-Cutting Symptom Measure, a 23-item self-report scale of symptoms that cut across 13 diagnostic domains (e.g., depression, anger, mania, anxiety, psychosis, etc.). Respondents are directed to rate the intensity of each symptom within the past 7 days on a 5-point scale ranging from 0 (none/not at all) to 4 (severe/nearly every day).

**4.2.3. Psychological well-being** will be measured using the Ryff Scales of Psychological Well-Being (SPWB), an 18-item self-report scale that assesses 6 domains of well-being: autonomy, environmental mastery, personal growth, positive relations with others, purpose in life, and self-acceptance. Respondents are directed to rate their agreement level with each item on a 7-point scale ranging from 1 (strongly agree) to 7 (strongly disagree).

## 4.3. Ecological Momentary Assessment

EMA assessments will be programmed and collected using MetricWire, a HIPAA-compliant EMA program that can coordinate sending mass text and email queries within a predetermined time-window. MetricWire collects de-identified responses using subject ID numbers. The program pushes assessment notifications to each subject's smartphone. Subject responses are then submitted to an encrypted server. MetricWire can automatically respond to invalid responses (e.g., numeric values outside the range of possible responses), filter multiple responses, and send standardized information to subjects based on predetermined response criteria (e.g., sending crisis hotline information for subjects indicating severe suicide ideation). Subjects will receive 4 EMA prompts per day on the 14 consecutive days coinciding with active treatment. EMA prompts will be sent at randomly selected times between 8 AM and 11 PM. EMA prompts will assess mood state, suicide ideation, PTSD symptom severity, emotion regulation strategies, location, and social context.

**4.3.1. Mood state** will be measured using a short form of the Positive and Negative Affect Scale (PANAS), a self-report scale that assesses positive and negative emotional states. Respondents are directed to rate the extent to which they are currently experiencing positive emotions and negative emotions.

**4.3.2. Suicide ideation** will be assessed using the first 5 items of the Scale for Suicide Ideation (SSI), described above in Section 4.1.1. The first 5 items assess intensity of the wish to live, wish to die, balance of the wish to live and wish to die, active suicide ideation, and passive suicide ideation.

**4.3.3. PTSD symptom severity** will be assessed using the NSESS, described above in Section 4.2.1.

**4.3.4. Location** will be assessed with a checklist that directs subjects to indicate their current location: home, work, school, friend's residence, family member's residence, bar/tavern/pub, indoor public space (e.g., grocery store, shopping center, gym), or outdoor public space (e.g., park, swimming pool). These items were selected to assess subjects' physical location.

**4.3.5. Social context** will be assessed with a checklist that directs subjects to indicate if the following types of people are within their immediate environment: no one (i.e., alone), romantic partners, non-partner family members, friends, coworkers, neighbors, acquaintances, and strangers. These items were selected to assess physical proximity to others.

#### 4.4. Covariates

**4.3.1. Psychiatric diagnosis** will be measured using a combination of (a) the Diagnostic Interview for Anxiety, Mood, and OCD and Related Neuropsychiatric Disorders (DIAMOND), (b) the American Psychiatric Association Disorder-Specific Severity Measures, and (c) the Adjustment Disorder New Module 8.

**4.3.1.1. Diagnostic Interview for Anxiety, Mood, and OCD and Related Neuropsychiatric Disorders (DIAMOND).** The DIAMOND is an empirically-supported structured diagnostic interview that assesses the most common mood, anxiety, and trauma-related psychiatric disorders in mental health.

**4.3.1.2. American Psychiatry Association (APA) Disorder-Specific Severity Measures.** The APA Disorder-Specific Severity Measures include a collection of self-report scales that assess the frequency of symptoms associated with commonly occurring psychiatric disorders. In the present study, we will use the Disorder-Specific Severity Measures for depression, specific phobia, social anxiety disorder, panic disorder, agoraphobia, generalized anxiety disorder, dissociative symptoms, and substance use.

**4.3.1.3. Adjustment Disorder New Module 8 (ADNM-8).** The ADNM-8 is an 8-item self-report scale that assesses recent exposure to a range of non-traumatic life stressors (e.g., divorce/separation, family conflicts) and frequency of symptoms associated with an adjustment disorder.

[figure not shown]
**4.3.2. Trauma exposure** will be measured using the Life Events Checklist for DSM-5 (LEC-5), an 18-item self-report scale that assesses exposure to a range of potentially traumatic events, and several features of the most stressful or upsetting event (e.g., potential for injury or death, involvement of sexual violence).

Assessment Measures	Screen	Eligibility	Pre-Tx	Tx	FU1	FU2
					Week	
			1	1-2	26	52
Primary Outcomes						
Scale for Suicide Ideation	S	I	E	E	S	S
Self-Injurious Thoughts and Behaviors Interview-Revised	S	I	E	E	S	S
Secondary Outcomes						
National Stressful Events Survey PTSD Short Scale	S	I	E	E	S	S
DSM-5 Self-Rated Level 1 Cross-Cutting Symptom Measure	S				S	S
Scales of Psychological Well-Being	S				S	S
Covariates						
Severity Measure for Depression	S					
Severity Measure for Social Anxiety Disorder	S					
Severity Measure for Specific Phobia	S					
Severity Measure for Panic Disorder	S					
Severity Measure for Agoraphobia	S					
Severity Measure for Generalized Anxiety Disorder	S					
Severity of Dissociative Symptoms	S					
Level 2 Cross-Cutting Symptom Measures, Substance Use	S					
Adjustment Disorder New Module 8	S					
Mini International Diagnostic Interview		I				
Life Events Checklist for DSM-5	S					
Positive and Negative Affect Scale			E	E		
Coping Strategies			E	E		

S=Self-Report, I=Interview, E=Ecological Momentary Assessment

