military or veteran samples being 6 months for individual treatment (Morland et al., 2014; Resick et al., 2017) and 1 year for group treatment (Resick et al., 2015). Clinical improvement and recovery rates tend to be higher among patients who complete CPT compared to those that drop out of treatment early (Resick et al., 2008). Data also suggest that PTSD outcomes are moderated by session frequency, such that CPT sessions spaced closer together yield better effects than CPT sessions that are spaced further apart (Gutner, Suvak, Sloan, & Resick, 2016).

In addition to reducing PTSD symptoms, recent studies indicate CPT is also associated with significant short-term reduction in suicide ideation (Bryan et al., 2016; Gradus, Suvak, Wisco, Marx, & Resick, 2013; Resick et al., 2017), potentially due to its effects on PTSD and depression symptom severity (Bryan et al., 2016; Gradus et al., 2016). In several of these studies, suicide ideation increased in severity again several months after the conclusion of therapy, however, suggesting a period of increased vulnerability for suicide. Enhancing CPT with procedures that have been shown to significantly reduce suicidal thoughts and behaviors could serve to further reduce suicide risk during and after treatment completion.

One such procedure is the crisis response plan (CRP), a collaborative, patient-centered intervention that is typically handwritten on an index cards and focuses on several key components: (1) warning signs, (2) self-regulatory strategies, (3) reasons for living, (4) sources of social support, and (5) professional and crisis services. An example CRP is displayed in the figure to the right. In a randomized clinical trial previously conducted by our team, acutely suicidal patients who received a CRP showed significantly faster declines in suicide ideation and were 76% less likely to attempt suicide during the 6-month follow-up as compared to treatment as usual (Bryan et al., 2017a). Subsequent research has found that the inclusion of reasons for living section within the CRP is also associated with significant increases in positive psychological states like optimism and hope (Bryan et al., 2017b), suggesting this component may be acting upon unique mechanisms that are not influenced by other interventions.

Warning Signs: pacing feeling irritable thinking "it'll never get better"

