### **3.8. Sample Size Estimation**

The primary outcome, suicide ideation, will be assessed up to 4 times: baseline, 2 weeks, 26 weeks, and 52 weeks). We will analyze data from the full sample and also conduct separate analyses for two subgroups of interest: those with suicide ideation at baseline and those without suicide ideation at baseline. Our primary planned analyses entail slope comparisons for suicide ideation scores.

Our assumptions for sample size estimation were based on previous research conducted by our team. In two separate pilot studies of our two-week treatment program, 50-70% of participants reported suicide ideation at baseline. We used this range to estimate the percentage of participants expected to report suicide ideation at baseline. We also based estimates on the results of a published RCT comparing the CRP to treatment as usual (Bryan et al., 2017a), which found small to moderate differences in suicide ideation between treatment groups over time ( $0.3 < d < 0.7$ ). We used this range to estimate a lower bound for the anticipated effect size (i.e.,  $d=0.3$ ).

Assuming a two-tailed  $\alpha < .05$ , a within-between interaction (i.e., treatment x time), a small correlation ( $r=0.1$ ) among repeated measures, a sample size of 112 ( $n=66$  per group) provides 80% power to detect an effect size equivalent to  $d=0.3$ . To account for expected attrition (~25%) and missing data (participants completing only 3 of 4 scheduled assessments), we will aim to enroll a total of  $N=150$  ( $n=75$  per arm) eligible participants, which provides 86% power to detect an effect size equivalent to  $d=0.3$ . Assuming two-thirds of the sample report suicide ideation at baseline—a rate comparable to our pilot studies—we will have 80% power to detect a minimum effect size of  $d=0.38$  among participants endorsing suicide ideation at baseline. Because we expect to consent and screen approximately 5 veterans to identify each eligible participant who consents to treatment, we will therefore enroll a total of 750.

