## **6. Data Analysis**

Prior to statistical analyses, we will visually inspect data to ascertain distributional properties and determine if data meet the assumptions for each of our planned analyses. Based on our previous studies, we expect the primary outcome (suicide ideation) to be positively skewed. If true for this study, we will consider and evaluate the most appropriate method for approaching each analysis (e.g., data transformations, bootstrapped confidence intervals, use of generalized linear modeling). We anticipate having up to 50% missing data from EMA and up to 30% missing data from follow-up. We will first use Little's test to determine if the missing data are ignorable (i.e., missing completely at random or missing at random). If the missing data are not ignorable, we will use multiple imputation. The number of imputed datasets will be determined based on the percent of data that are missing and contemporary recommendations. Our primary outcome for Aim 1 is suicide ideation, measured using the SSI total score.

For H1, we will use generalized linear mixed models with SSI total score as the outcome variable and treatment, time, and treatment x time entered as predictors. We will first assess change in SSI scores across the four primary time points: baseline, posttreatment, 6 months, and 12 months. H1 will be supported if there is a statistically significant treatment x time interaction indicating a faster reduction in suicide ideation among participants receiving CPT+CRP. Sensitivity analyses will then be conducted with SSI total scores from the initial screening and the eligibility interview added to the model, thereby enabling us to determine if reductions in suicide ideation coincided with the start of treatment and ruling out the possibility that observed differences between groups is attributable to pre-treatment temporal trends (e.g., participants in one group showing reductions in suicide ideation that precede the initiation of treatment).

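### Pre-randomisation depression and PTSD severity have no role in the H1 and H2 models; adding them by time costs little, may gain a little precision, and would support the missing-data assumption

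*Combined protocol and SAP*

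**What the plan says.** **What is collected.** The table in Section 4.4 lists "Severity Measure for Depression" under Covariates, as a self-report taken at screening only. NSESS is classed as a secondary outcome. It is self-reported at screening, marked as an interview item at eligibility, marked as EMA before and during treatment, and self-reported again at both follow-ups. Section 5 places randomisation after the screening survey and the eligibility interview, so the screening value of each measure precedes allocation.

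**What is modelled.** Section 6 fits the four-visit SSI total score with "treatment, time, and treatment x time entered as predictors". The EMA model has the same three terms, and H2 repeats both models in participants with ideation at baseline. No measure listed under Section 4.4 is given a role in any of these analyses.

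**What links severity to ideation.** Section 2 says that the fall in ideation seen with CPT is "potentially due to its effects on PTSD and depression symptom severity".

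**Missing data.** Section 6 expects up to 30% missing at follow-up and up to 50% missing in EMA. It allows for multiple imputation but names no imputation variables.

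**The concern.** A variable is labelled a covariate and the plan never says what it is a covariate for. The stated models leave it out, and any later decision to adjust would be made with the data in hand.

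Two things could be at stake. First, if baseline severity predicts how SSI changes, that variation stays in the error term of the treatment x time test on which H1 and H2 are judged. Second, the mixed model rests on missing at random given treatment, time and observed SSI. If severity is related both to dropout and to the later course of ideation, conditioning on a pre-randomisation measure of it makes that assumption easier to defend.

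**Working it through.** **Inputs, all from Section 3.8 except the last**
- Two-sided 5% level ("Assuming a two-tailed").
- Test and correlation: "a within-between interaction (i.e., treatment x time), a small correlation" of r = 0.1 among repeated measures.
- d = 0.3, described as "We used this range to estimate a lower bound for the anticipated effect size"; entered as f = d/2 = 0.15.
- Four visits: the outcome "will be assessed up to 4 times: baseline, 2 weeks, 26 weeks, and 52 weeks".
- "a sample size of 112" for 80% power. The accompanying 66 per group would make 132, not 112; I use 112 because it reproduces.
- R², the share of the variance of SSI change explained by the two covariates by time: not in the documents, so assumed from 0 to 10%.

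**Step 1. Reproduce the plan's figures.** For the within-between F test, λ = N·m·f²/(1 − r), with m − 1 and (N − 2)(m − 1) degrees of freedom.
- N = 112, m = 4: λ = 112 × 4 × 0.0225 / 0.9 = 11.2 on 3 and 330 df. Power is 80.7%, agreeing with the stated 80%.
- 112 / (1 − 0.25) = 149.3, rounded up to 150, as stated.
- N = 150, m = 3: λ = 150 × 3 × 0.0225 / 0.9 = 11.25 on 2 and 296 df. Power is 85.7%, agreeing with the stated 86%.

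**Step 2. Main effects only.** A person-level term that is the same at every visit cancels from a change between visits. This was checked by generalised least squares for the baseline-to-last-visit contrast (N = 150, four visits, compound symmetry, covariate equally associated with SSI at every visit).
- Complete data: the standard error is 0.2191 with and without the covariate at r = 0.1, and 0.1633 in both cases at r = 0.5. There is no gain.
- 30% of participants missing both later follow-ups, r = 0.1: 0.2435 without and 0.2418 with the covariate, a ratio of 0.993, or about 0.7%.

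**Step 3. Covariates by time.** Explaining a share R² of the variance of change multiplies λ by 1/(1 − R²). Two covariates and their time terms are charged for by replacing N with N − 2 in λ and lowering the denominator df to (112 − 4) × 3 = 324. So λ = 11.2 × (110/112)/(1 − R²).

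| Assumed R² | λ after charge | Power, no charge | Power, charged |
|---|---|---|---|
| 0 | 11.00 | 80.7% | 79.9% |
| 2% | 11.22 | 81.5% | 80.7% |
| 3% | 11.34 | 82.0% | 81.2% |
| 5% | 11.58 | 82.8% | 82.1% |
| 10% | 12.22 | 85.0% | 84.3% |

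Break-even is where (110/112)/(1 − R²) = 1, that is R² = 2/112, about 1.8%.

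The basis that reproduces 86% (N = 150, three visits) gives the same picture. With λ = 11.25 × (148/150)/(1 − R²) on 2 and 292 df, power is 85.2, 86.0, 86.3, 87.1 and 88.9%, against 85.7% unadjusted.

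**Step 4. What such an R² requires.** With equal variances at two visits, R² for the change between them is Δ²/(2(1 − r)), where Δ is the difference between visits in the correlation of a combined severity score with SSI. At r = 0.1, Δ = √(1.8 × R²), which gives 0.23, 0.30 and 0.42 for R² of 3, 5 and 10%.

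**The case against.** The strongest objection is that nothing in the documents shows there is any precision to gain. A reader might infer from Section 2 that, on the plan's own account, baseline depression and PTSD severity should predict change in SSI. The passage does not say that. It suggests tentatively that CPT lowers ideation by changing these symptoms during treatment, which is a statement about a route of effect and not about baseline level as a predictor. This objection stands. The shifts in correlation in Step 4 are demanding, and if the association is constant over visits the gain is nil.

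The scaling by 1/(1 − R²) is also approximate. With four visits there are three independent time contrasts, and two covariates can explain variance in at most two of them. The formula assumes that the treatment effect follows a time profile where they do. Section 6 also expects skewed SSI scores and leaves transformation or a generalised model open, whereas the arithmetic is linear and Gaussian. Both points stand as limits on the figures.

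On missing data, the planned model already uses every observed SSI score, imputation is provided for, and no passage says that severity predicts dropout. That keeps the second benefit a matter of plausibility and leaves it without a number. It does not remove it, because the present model conditions on nothing about the participant beyond treatment and SSI.

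Finally, an unadjusted treatment x time comparison is valid in a randomised trial. That is right, and the point is one of efficiency and prespecification only.

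**Conclusion.** The concern holds in a limited form. Both measures are in hand before randomisation, one is labelled a covariate, and no H1 or H2 model uses either. Prespecifying them by time is a cheap improvement whose effect on power runs from a loss of about 0.8 points (R² = 0), through no change at about 2%, to gains of about 0.5, 1.4 and 3.6 points at 3, 5 and 10%. These figures rest on assumed R² values, a linear model and the plan's r = 0.1. The further benefit, a more credible missing-at-random assumption, cannot be sized from the documents.

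A reader might go further and conclude that the plan throws away precision it has already paid for, or that the primary comparison is flawed without adjustment. The documents support neither: the gain may be zero, and randomisation protects the unadjusted comparison. This is a desirable refinement, not a defect that threatens the trial.

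**What to change.** In Section 6, name two covariates: the depression severity score from screening and the self-report NSESS score from screening. State the NSESS assessment explicitly, because the scale is also taken at eligibility and before treatment. Enter each as a main effect and by time in the four-visit and EMA models for both H1 and H2, and include both in any imputation model. Fix the list before outcome data are examined, and report the model without them as a sensitivity analysis.

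The cost is a sentence or two of plan text and no new data. The statistical price is a few degrees of freedom, up to about one point of power at N = 112 if the covariates explain nothing. It is somewhat heavier in the H2 subgroup: two-thirds of 150 is about 100 participants, so the break-even R² is about 2/100 = 2%.

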## 5. Detailed Study Procedures

The flow of participants through the study procedures are displayed in the figure below:

Potential participants will be recruited via a combination of methods outlined above in Section 3.2.1 and will complete an initial self-report screening to assess for the presence and intensity of psychological symptoms associated with PTSD and other common comorbid conditions (e.g., depression, panic disorder), and presence and intensity of suicide ideation. Potential participants will also be asked about their military service history. The entire screening process is expected to take less than 30 minutes to complete. Based on their responses to survey items, potential participants may be invited to share their contact information, which will be emailed to a member of the research team.

A researcher will then contact the potential participant to complete an eligibility interview conducted by phone or Zoom. During this interview, clinician-administered interviews will be completed to confirm the potential participant's primary diagnosis, to assess level of suicide risk (i.e., determining if there is imminent risk warranting immediate intervention and assistance), and to confirm prior military service. Individuals meeting eligibility criteria will then be given additional information about the study procedures and will be able to ask any questions about the study's procedures. The eligibility interview is expected to take approximately 1 hour to complete.

Those agreeing to continue their participation will be assisted in downloading the EMA data collection app to their smartphone, and will receive instructions on how to use the app. Finally, they will be

randomized to one of the two treatment groups and scheduled for their first therapy session. Participants will participate in one hour of psychological treatment per day for 12 consecutive business days (i.e., excluding weekends), for a total time commitment of 12 hours. They will also complete EMA surveys every day for 14 consecutive days (i.e., including weekends). EMA assessments will require 20 minutes per day, for a total of approximately 4.5 hours.

After completing treatment, participants will be given instructions on how to remove the EMA data collection app from their smartphones. Participants will be contacted 6 and 12 months postbaseline to complete the scheduled follow-up assessments. Each follow-up assessment is expected to take approximately 15 minutes to complete.

